9.6.3.2. Secondary Endpoints Analysis

ADEs per severity

A descriptive analysis with 95% exact Clopper-Pearson confidence interval of mild, moderate and severe ADEs will be provided in the FAS, by treatment groups and overall.

AEs

All AEs will be described in the FAS, for each System Organ Class (SOC) and Preferred Term (PT) class using MedDRA (Medical Dictionary for Regulatory Activities) terminology, by treatment groups and overall.

DDs

All DDs will be described in the FAS, by treatment groups and overall.

| | |
|--|--------------|
| 2022.08.11_RGnCON_Prot_Final_V2.0_clean_public | Page 48 / 82 |
|--|--------------|

Secondary performance analyses

The secondary performance analyses will be performed in the FAS by treatment groups, excluding data that would be collected after the following intercurrent event: treatment group switch during follow-up.

Imputation of missing data will be handled by the mixed model (details will be provided in the Statistical Analysis Plan).

The analyses will be performed as follows:

- For the evolution of the below parameters, the following timepoints will be compared: (D0 after treatment - D0 before treatment, D7 before treatment - D0 before treatment, D7 after treatment - D0 before treatment, and D52 – D0 before treatment) and a mixed effect regression model will be used with a patient random effect. Group effects (5 Hz vs 10Hz), period effects (D0 before, D0 after, D7 before, D7 after and D52) and the group-by-period interaction will be added as fixed effects. The stratification variables will be added in the model as covariates.
 - Automated oculomotor and oculopostural functions:
 - Convergence, evaluated with the Near Point of Convergence (NPC) (>5 cm vs ≤5 cm)
 - Deviation as evaluated with the cover test (normal fixation or light restitution movement or important restitution movement or deviated eye without restitution movement)
 - Horizontal deviation as evaluated with the Maddox rod test (orthophoria or exophoria or esophoria and measure in diopter)
 - Vertical deviation of the right eye as evaluated with the Maddox rod test (orthophoria or hypophoria or hyperphoria and measure in diopter)
 - Vertical deviation of the left eye as evaluated with the Maddox rod test (orthophoria or hypophoria or hyperphoria and measure in diopter)
 - Balance function:
 - Statokinesigram area (m²)
 - Difference between left distribution and right distribution (%)

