#### 6.2.2. Secondary performance endpoints

According to section 9.5.4.2 of the Protocol, the following endpoints will be used to address Secondary performance objectives:

- Automated oculomotor and oculopostural functions will be used as recorded in the eCRF, before and after treatment session at D0 and D7 and then at D52:
  - Convergence, evaluated with the measure of the Near Point of Convergence (NPC)
  - Deviations:
    - Cover test
      - Normal fixation of both eyes
      - Abnormal with at least one eye
    - Maddox rod test:
      - Horizontal deviation (yes/no)
      - Vertical deviation right eye (yes/no)
      - Vertical deviation left eye (yes/no)
- Balance function will be used as recorded in the eCRF, before and after treatment session at D0 and D7 and then at D52:
  - Patient's eyes opened

- Statokinesigram area (mm^2)
- Left distribution (%)
- Right distribution (%)
- Patient's eyes closed
  - Statokinesigram area (mm^2)
  - Left distribution (%)
  - Right distribution (%)
- Rombert quotient (RQ)

The Romberg quotient is the ratio between the statokinesigram area (mm^2) with closed eyes (CE) and the statokinesigram area (mm^2) with opened eyes (OE), it will be calculated as follow :

$$RQ = CE/OE.$$

- Statokinetic distribution index (SKDI)

The stato-kinetic distribution index (SKDI) is the result of the STKG area multiply by the ratio of support distribution it will be calculated as follow:

$$SKDI (\text{mm}^2) = STKG \text{ area } (\text{mm}^2) \times (D/d^*)$$

\*D : Highest distribution value (%)

d : Lowest distribution value (%)

- TMT A&B before treatment session at D0 and after treatment session at D7:
  - TMT – A
    - Time to perform the task will be derived as:  
$$\text{Time to perform the task (in second)} = \text{minutes} * 60 + \text{second.}$$
    - Number of errors (will be used as recorded in the eCRF)
  - TMT –B
    - Time to perform the task will be derived as:  
$$\text{Time to perform the task (in second)} = \text{minutes} * 60 + \text{second.}$$
    - Number of errors (will be used as recorded in the eCRF)
  - TMT – B - A
    - Time to perform the task will be derived as:  
$$\text{Time to perform the task (in second)} = \text{Time to perform the task B} - \text{Time to perform the task A}$$
    - Number of errors will be derived as:  
$$\text{Number of errors} = \text{Number of errors B} - \text{Number of errors A}$$

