#### 8.5.1.1. Automated oculomotor and oculopostural functions and balance function

For the evolution of parameters of oculomotor and oculopostural functions and balance function defined in Section 0, the following timepoints will be compared: (D0 after treatment - D0 before treatment, D7 before treatment - D0 before treatment, D7 after treatment - D0 before treatment, and D52 – D0 before treatment). A mixed effect regression model (logistic model for a categorical parameters and a linear model for continuous parameters) will be used with a patient random effect. Group effects (5 Hz vs 10Hz), period effects (D0 before, D0 after, D7 before, D7 after and D52) and the group-by-period interaction will be added as fixed effects. The stratification variable gender (male/female) will be added in the model as covariates.

Note: the stratification variable concussion history within 6 months prior to inclusion (yes/no) will not be added in the model as too few patients had concussion history (cf. data review minutes of 18/07/2023).

The following template will be used for continuous parameters.

	Group of treatment		
Ref = D0 before treatment	RGn550 5Hz N=xx	RGn550 10Hz N=xx	Difference
Endpoint XXX at D0 after treatment			
Adjusted mean	x.xx	x.xx	x.xx
95% CI	x.xx ; x.xx	x.xx ; x.xx	x.xx ; x.xx
p-value	.	.	0.xxx
Endpoint XXX at D7 before treatment			
Adjusted mean	x.xx	x.xx	x.xx
95% CI	x.xx ; x.xx	x.xx ; x.xx	x.xx ; x.xx
p-value	.	.	0.xxx
Endpoint XXX at D7 after treatment			
Adjusted mean	x.xx	x.xx	x.xx
95% CI	x.xx ; x.xx	x.xx ; x.xx	x.xx ; x.xx
p-value	.	.	0.xxx
Endpoint XXX at D52			

		Group of treatment		
Ref = D0 before treatment		RGn550 5Hz N=xx	RGn550 10Hz N=xx	Difference
Adjusted mean		x.xx	x.xx	x.xx
95% CI		x.xx ; x.xx	x.xx ; x.xx	x.xx ; x.xx
p-value		.	.	0.xxx

From an mixed model including treatment (p=0.xxx), visit (p=0.xxx), treatment-by-visit interaction (p=0.xxxx) as fixed effects and variable xxx as random effect, variableyyy (p=0.xxx) as baseline covariate.

The following template will be used for categorical parameters.

	RGn550 10Hz vs RGn550 5Hz at visit 1	RGn550 10Hz vs RGn550 5Hz at visit 2	visit 2 vs visit 1 at RGn550 10Hz	visit 2 vs visit 1 at RGn550 5Hz
Endpoint XXX				
Odds ratio	X.X	X.X	X.X	X.X
95% CI	[X.X ; X.X]	[X.X ; X.X]	[X.X ; X.X]	[X.X ; X.X]

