From an mixed model including treatment (p=0.xxx), visit (p=0.xxx), treatment-by-visit interaction (p=0.xxxx) as fixed effects, variable xxx as random effect and variableyyy (p=0.xxx) as baseline covariate.

In addition, the following analyses will be performed for exploratory purpose:

- The NPC measurement will also be analyzed in the subgroup “NPC > 5 at D0 before treatment”.
- The Maddox rod horizontal will also be analyzed in the subgroup “Horizontal deviation at D0 before treatment”.
- The Maddox rod vertical - left eye will also be analyzed in the subgroup “Vertical deviation at D0 before treatment”
- The Maddox rod vertical - both eyes will also be analyzed in the subgroup “Vertical deviation at least one eye at D0 before treatment”.

Note: the Maddox rod vertical – right eye will not be analyzed in the subgroup “Vertical deviation at D0 before treatment” as too few patients were included in this subgroup (cf. data review minutes document of 18/07/2023).

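### In the exploratory Maddox subgroups every patient has a deviation at D0, so yes/no contrasts with D0 cannot be estimated; in the NPC > 5 subgroup only the per-arm change from D0 is distorted

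*SAP*

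**What the plan says.** **Subgroups.** SAP section 5 defines subgroups by the result at D0 before treatment: NPC above 5, a horizontal Maddox deviation, and a vertical deviation of the left eye, the right eye or at least one eye. SAP 8.5.1.1 then analyses each test inside the subgroup selected on that same test, and labels this exploratory. For example, "The Maddox rod horizontal will also be analyzed in the subgroup" with a horizontal deviation, and "The NPC measurement will also be analyzed in the subgroup" with NPC above 5. The left-eye and both-eyes vertical tests are handled the same way. The right-eye subgroup was dropped as too small.

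**Outcomes.** SAP 6.2.2 lists "Horizontal deviation (yes/no"), "Vertical deviation left eye (yes/no") and the matching right-eye item. It gives no both-eyes outcome. For NPC it lists "Convergence, evaluated with the measure of the Near Point of Convergence (NPC").

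**Model.** SAP 8.5.1.1 uses a "logistic model for a categorical parameters and a linear model for continuous parameters", with a patient random effect. Fixed effects are arm, five periods (D0 before treatment is one of them), their interaction, and gender. Later periods are compared with D0 before treatment. The continuous template shows an adjusted mean with interval for each arm, and the arm difference with interval and p-value. The categorical template shows four odds ratios: the arms at visit 1, the arms at visit 2, and visit 2 against visit 1 in each arm. No different model is given for the subgroups.

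**Competing descriptions.** Protocol 9.6.3.2 lists "Horizontal deviation as evaluated with the Maddox rod test (orthophoria or exophoria or esophoria and measure in diopter"). SAP section 10 calls the horizontal variable a score.

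**The concern.** A logistic model that compares each visit with D0 needs both yes and no responses at D0. Selecting patients because they were yes at D0 removes every no, in both arms. The software then either fails to converge or reports a very large coefficient whose value depends on where the iterations stopped.

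Selection also fixes the direction of change: a patient who starts at yes can only stay or improve. For a continuous outcome the model runs, but part of the fall from D0 is regression to the mean.

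The trial has no sham arm, and the protocol says symptoms typically resolve in 10 to 14 days. Per-arm improvement in these subgroups could therefore be read as device performance when some of it comes from the selection rule.

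**Working it through.** **The plan's own figures.** The plan gives none for these subgroups. Its one design figure, a 0.87 chance of at least one ADE in 50 patients at a rate of 0.04, reproduces (1 − 0.96^50 = 0.8701) but has no bearing here.

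**Step 1: yes/no Maddox, by argument.** With arm, period and interaction in the model, each arm has its own D0 logit, β. A patient who is yes at D0 contributes expit(β + b), where b is the patient effect. This rises with β for every b. No patient in the subgroup is no at D0, so nothing pulls β down, and the likelihood has no maximum at a finite β. The gender covariate does not change this, and neither does a larger sample. It follows that:
- each odds ratio of a later visit against D0 tends to 0;
- the 10 Hz versus 5 Hz odds ratio at D0 is undefined (infinite odds in both arms);
- visit and interaction tests that involve D0 are unreliable.

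If visit 1 in the categorical template is D0 before treatment, three of its four columns are affected.

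**Step 2: numerical check.** A random-intercept logistic model (arm by period, without gender) was fitted to one simulated data set of 12 patients per arm, all yes at D0. The size is assumed. The D0 logit was fixed at a common value in both arms and the rest maximised:

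| D0 logit | 1 | 2 | 4 | 6 | 8 | 10 | 15 | 20 |
|---|---|---|---|---|---|---|---|---|
| log-likelihood | −64.22 | −59.59 | −55.16 | −53.82 | −53.47 | −53.40 | −53.386 | −53.386 |

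It climbs to a plateau without a peak. An unselected data set peaks near 0.5 (−68.76 at 0, −68.40 at 0.5, −68.58 at 1, −70.21 at 2).

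In the selected data the arm odds ratios at the four later visits settle: 1.95, 1.95, 24.61 and 13.24 with the D0 logit at 10, and 1.96, 1.96, 24.87 and 13.35 at 20. They are finite, which is the point of the check. No arm effect was simulated, so the large values also show how imprecise such small groups are.

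**Step 3: direction of change for yes/no.** With no true change and a 50% yes rate before selection, the later yes rate among those who were yes at D0 is 59%, 70% or 82% for an assumed patient-effect SD of 1, 2 or 4 on the logit scale. The drop from 100% is selection alone.

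**Step 4: NPC > 5, continuous.** With no true change,

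expected fall = (1 − ρ) × SD × φ(a) / (1 − Φ(a)), where a = (5 − mean) / SD.

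The documents give no mean, SD or reliability ρ, so these are assumed. For mean 6 cm and SD 3 cm: a = −0.333, φ(a) = 0.377, 1 − Φ(a) = 0.631, ratio 0.598. The fall is then (1 − ρ) × 3 × 0.598, which gives 0.18, 0.36 and 0.54 cm at ρ = 0.9, 0.8 and 0.7. The extremes over the assumed grid are:
- mean 8, SD 2, ρ = 0.95: 0.01 cm;
- mean 5, SD 4, ρ = 0.70: 0.3 × 4 × 0.798 = 0.96 cm.

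**Step 5: arm difference for NPC.** In 4,000 simulated trials of 50 patients (mean 6, SD 3, ρ = 0.8, no effect), the within-subgroup change averaged −0.364 cm. The difference in change between arms averaged −0.009 cm (simulation SE 0.011). Selection on a pre-treatment value acts equally on both randomised arms.

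**The case against.** The strongest reply is that the SAP may not intend a yes/no outcome here. SAP 8.5.1.1 does not say which Maddox variable enters the subgroup models, section 10 speaks of a score for the horizontal test, and the protocol has a dioptre measure. If dioptres are modelled, the model is linear and separation does not arise. This stands as a real ambiguity. It does not dispose of the point: 6.2.2 defines only yes/no, section 10 uses the word score for the horizontal test alone, and a dioptre analysis referenced to D0 in patients selected for deviation has the same regression to the mean as NPC.

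Three other replies also stand. The analyses are exploratory in a pilot whose primary endpoint is safety. The continuous template attaches its p-value to the arm difference, which is not biased by the selection. Per-arm change is already confounded with natural recovery, and the protocol acknowledges that the placebo effect is uncontrolled.

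A reader might go further and infer that the Maddox analysis fails as a whole, or that the NPC subgroup comparison of the arms is biased. The documents do not support either reading. The full-analysis-set models involve no such selection, arm odds ratios at later visits remain estimable in the subgroups, and the NPC arm contrast is unbiased. Nor does the NPC subgroup share the separation: that would follow only if NPC were dichotomised at 5 cm, as in the protocol, whereas the SAP analyses the measurement.

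**Conclusion.** The point holds on the SAP's own definitions, within limits. For Maddox horizontal and left-eye vertical as yes/no, contrasts with D0 have no finite estimate; this follows from the subgroup definition and needs no assumed number. The same applies to the both-eyes analysis if it means a deviation in at least one eye, which 6.2.2 does not say. If dioptres are meant, the defect changes to regression to the mean in the per-arm change.

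For NPC > 5, the per-arm change is overstated by an unknown amount; 0.01 to 0.96 cm covers the assumed ranges, and all of it rests on assumed inputs. The primary endpoint and the main performance models are not touched. This should be corrected, but it does not threaten the trial's main conclusions.

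**What to change.** - State in SAP 6.2.2 and 8.5.1.1 which Maddox variable is used in the subgroups, align section 10 with it, and define the both-eyes outcome. If dioptres are used, say how exophoria and esophoria are signed.
- For yes/no outcomes, take D0 before treatment out of the response and report 10 Hz versus 5 Hz at the post-D0 visits only. Where a later cell is also all yes or all no, give counts with exact intervals.
- For dioptres and NPC, model the post-D0 visits with the D0 value as a covariate and report the arm contrast. Either omit the per-arm change from D0 or label it as affected by selection and natural recovery.

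The cost is SAP wording and minor programming. No new measurement is needed, since the protocol's Maddox procedure already quantifies deviation with prisms. The downside is that these exploratory subgroups will give no model-based change from D0.

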### 8.5.1.2. Executive function (TMT A&B)

For the evolution of executive functions defined in Section 0, the following timepoints will be compared: (D0 before treatment – D7 after treatment) and a mixed effect regression model (logistic model for a categorical parameter and a linear model for continuous parameter) will be used with a patient random effect. Group effects (5 Hz vs 10Hz), period effects and group-by-period interaction will be added as fixed effects. The stratification variable gender (male/female) will be added in the model as covariates.

The same template as above (i.e. for continuous parameters) will be used.

### 8.5.1.3. Concussion syndrome symptoms (SCAT5)

For concussion syndrome symptoms (SCAT5) functions defined in Section 0, the following timepoints will be analyzed (D0 before treatment, D7 before treatment, D14 and D52), a mixed linear regression model will be used with a patient random effect. Group effects (5 Hz vs 10Hz), period effects and

group-by-period interaction will be added as fixed effects. The stratification variables and SCAT5 baseline will be added in the model as covariates.

The same template as above will be used.

In addition, for exploratory purpose, the concussion syndrome symptoms (SCAT5) will also be analyzed in the subgroup “Number of previous concussions”.

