9.2.1.1.3. Symptoms

In the acute phase, concussion is an evolving injury with rapidly changing clinical signs and symptoms [2].

These symptoms can be categorized into [1–3, 6, 7]:

- Somatic symptoms, such as:
 - Headache
 - Vision changes including blurred vision, light sensitivity, difficulty reading and convergence dysfunction
 - Coordination disorders
 - Disturbance in balance
 - Insomnia
 - Somnolence
 - Drowsiness

| | | |
|--------|---|--|
| RGnCON | Clinical Investigation Plan Version 2.0 - 11 August 2022 | |
|--------|---|--|

- Cognitive impairment, such as:
 - Feeling like in a fog
 - Disorientation
 - Difficulty concentrating
 - Slowed reaction time
 - Loss of consciousness
 - Amnesia
 - Neurological deficit
- Emotional / behavioral changes such as:
 - Irritability
 - Lability

Altogether, this set of symptoms is called **concussion syndrome** [1, 6].

In adults, symptoms typically resolve in 10 to 14 days [2]. However, some may linger for weeks. Persistent post-concussion syndrome occurs when symptoms persist beyond 3 months [6].

Of note, well-trained and well-prepared sportspersons are thought to heal more rapidly [1, 4].

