9.2.1.1.4. Complications

Although the short-term vital prognosis is very good (mortality < 1%), the functional prognosis in the mid- and long-term is more uncertain. Indeed, approximately 10-20% of the patients will have long-lasting effects [3].

The literature on neurobehavioral sequelae and long-term consequences of exposure to recurrent head trauma is inconsistent. However, reported potential long-term problems include [1, 2]:

- Cognitive impairment
- Depression
- Chronic traumatic encephalopathy (although a cause-and-effect relationship has not yet been demonstrated between chronic traumatic encephalopathy and concussion).

Of note, well-trained and well-prepared sportsperson are thought to have less complications. Interestingly, concussions have been reported to be more severe in sportswomen than sportsmen [1].

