Following this, the patient will evaluate his/her symptoms using the **SCAT5 symptom evaluation tool**. The patient will rate the intensity of every symptom from 0 (none) to 6 (severe) using a form. This will allow to calculate the total number of symptoms (out of 22) and the symptom severity score (out of 132) (see Appendix 12.3).

A **blood sample** will also be obtained from the patients by a nurse. The blood sample analysis will be performed by Montpellier Neuroscience Institute (*Institut de Neuroscience de Montpellier*) following the institute standard practice.

During the visit, the patients will be **randomized** in a 1:1 ratio to the 5 Hz group or 10 Hz group using the centralized Interactive Web Response System (IWRS) incorporated into the eCRF. A block randomization method will be used. Only patients will be blinded to their assigned treatment.

Depending on their assigned group, the patients will then be **treated** with one of the 5 Hz RGn550 devices or one of the 10 Hz RGn550 devices for 20 min. To perform the treatment, the principal investigator will follow the below instructions:

- Make the patient comfortable.
- Install the helmet on the patient's head, taking care not to bump it with the modules.
- Lightly tighten the soft helmet holding wire and check the positions of the modules. Each module can be moved slightly to adjust its position.
- On the control unit, in the menu on the left, choose the option 'Program' and choose the proposed treatment
- Finally press the red arrow to start the treatment.

A countdown is displayed on the screen indicating the time remaining until the end of the treatment session. At each treatment session, the principal investigator will fulfil a treatment sheet associated with the used device and mention the number of the treated patient, date of treatment, number of

treatment session and duration of treatment. To stop the treatment, the principal investigator will press the red button with a cross inside that is displayed on the screen (a confirmation message will be displayed to avoid any manipulation error).

Following treatment, the investigators will:

- **Perform the following tests** following the methodology described above:
 - NPC
 - Cover test
 - Maddox rod test
 - Static stabilometric test
- **Collect any AEs and DDs** that occurred during the visit.

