9.6. Statistical Considerations

9.6.1. Sample Size Justification

For a sample size of 50 patients, the probability of observing at least one ADE will be 0.87 considering a probability of ADE of 0.04. The sample size calculation was performed with SAS® v9.4.

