9.6.3. Statistical Analysis

Full details related to statistical analysis will be provided in the Statistical Analysis Plan.

The statistical analysis will be performed using SAS® Viya v9.4 (or a more recent version).

The global significance level (type I error rate) will be set at $\alpha = 0.05$ (two-sided). Adjustment for multiplicity is not applicable for the primary endpoint and no adjustment for multiplicity is planned for secondary endpoints.

Continuous data will be described by the number of missing data, number of data analyzed, mean, standard deviation, median, Q1, Q3, minimum, maximum.

Categorical data will be described by the number of missing data, frequencies and percentages of patients in each modality. The percentage of patients will be calculated once missing data are excluded from the denominator.

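### SAP 8.5.1.3 pools one residual variance over SCAT5 visits whose spread should differ greatly and leaves the arm contrast unclear, so the per-visit p-values are unreliable on either main reading

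*SAP*

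**What the plan says.** - **Model.** SAP 8.5.1.3 states that "a mixed linear regression model will be used with a patient random effect", with group, period, group-by-period, the stratification variables and the SCAT5 baseline in the model. Protocol 9.6.3.2 has the same model without the baseline covariate, and SAP section 10 does not list that addition as a change.
- **Visits.** The visits analysed are "D0 before treatment, D7 before treatment, D14 and D52", so D0 is listed with the responses and is also the baseline covariate.
- **Contrast.** The text does not say which arm difference is reported. It refers back to the earlier template. In SAP 8.5.1.1 the template for continuous parameters takes the pre-treatment D0 value as reference and gives adjusted means, an arm difference, a 95% CI and a p-value at each later visit.
- **Expected course.** Protocol 9.2.1.1.3: "In adults, symptoms typically resolve in 10 to 14 days". Protocol 9.2.1.1.4: "approximately 10-20% of the patients will have long-lasting effects". Entry is within 72 hours of injury, so D14 is about day 14-17 after injury and D52 about day 52-55.
- **Error control.** Alpha is 0.05 two-sided, and "no adjustment for multiplicity is planned for secondary endpoints".

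Neither document gives an expected SCAT5 mean, SD, share at zero or effect size. Neither makes provision for unequal variance across visits.

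**The concern.** A random intercept with one residual variance assumes the same spread at every visit. SCAT5 cannot go below 0. If most patients recover, scores are widely spread at D0 and tightly packed near 0 by D52. Two things follow.

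1. When D52 is near 0, the change from D0 is roughly minus the D0 score. An arm difference in change then mainly restates which arm happened to start worse.
2. The pooled variance is too small for some contrasts and too large for others, so the CIs and p-values have the wrong width.

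Protocol 9.2.3 says that comparing the two arms will show which frequency is better for safety and performance. SCAT5 is the patient-reported symptom measure in that comparison, so a D52 difference produced by D0 imbalance could mislead the choice.

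**Working it through.** **The plan's own figure.** The only design figure is for safety: "For a sample size of 50 patients, the probability of observing at least one ADE will be 0.87 considering a probability of ADE of 0.04". Check: 1 - 0.96^50 = 0.8701, which agrees. There is no such figure for SCAT5, so everything below on its distribution is assumed.

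**Inputs from the documents.** 50 patients, randomised "in a 1:1 ratio to the 5 Hz group or 10 Hz group", hence 25 per arm; two-sided 5%; visits and model as above.

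**Step 1: one case by hand.** Assume D0 severity has SD 20 (mean 30), 85% are at zero by D52, unresolved patients have mean 10 and SD 7, and D52 is independent of D0.
- D52 mean = 0.15 × 10 = 1.5. D52 variance = 0.15 × (10² + 7²) - 1.5² = 22.35 - 2.25 = 20.1.
- Variance of D52 minus D0 = 20² + 20.1 = 420.1. D0 supplies 400/420.1 = 95% of it. The correlation of change with D0 is -20/√420.1 = -0.98.
- With a D0 SD of 12 instead: 144/164.1 = 88%, correlation -0.94.
- SD of the arm difference in change = √(2 × 420.1/25) = 5.80 (5.77 in simulation).
- The random-intercept model uses √(4σ²/25), where σ² is the pooled residual variance. In simulation this averaged 4.24, so σ² = 4.24² × 25/4 = 112. The model thus gives a patient's change a variance of 2 × 112 = 225, against the true 420.
- Real error of the 5% test = 2 × [1 - Φ(1.96 × 4.24/true SD)]:
  - D52: 1.96 × 4.24/5.77 = 1.44, error 15.0%.
  - D14 (50% at zero, true SD 5.98): 1.39, error 16.5%.
  - D7 (true SD 3.46): 2.40, error 1.6%.

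**Step 2: the SAP model, with gender and SCAT5 baseline included.** Null simulations, 25 per arm, complete data, 5,000-6,000 trials per row, D0 severity mean 30. The columns give the actual error of the nominal 0.05 test.

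| Assumed case | % at zero D7/D14/D52 | SD at D0/D7/D14/D52 | Change from D0: D7/D14/D52 | Share of D52 change contrast due to D0 imbalance | D0 as covariate only: D7/D14/D52 |
|---|---|---|---|---|---|
| Fast | 20/60/90 | 20.5/10.8/7.4/3.5 | .086/.158/.204 | 96% | .115/.040/.007 |
| Middle | 20/50/80 | 20.4/13.4/10.3/5.8 | .062/.110/.166 | 92% | .094/.046/.014 |
| Slow | 10/40/80 | 20.5/16.0/13.9/8.7 | .032/.057/.120 | 81% | .072/.051/.029 |
| Low D0 spread | 20/50/85 | 14.7/11.4/9.0/4.5 | .056/.082/.112 | 90% | .108/.054/.006 |
| High D0 spread | 20/50/85 | 25.5/15.6/11.6/5.7 | .066/.118/.191 | 95% | .103/.040/.015 |
| No floor (control) | 0/0/0 | 14.7/18.6/16.6/16.6 | .028/.020/.013 | 7% | .062/.040/.038 |

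Further runs under other assumed distributions widen the ranges to about 8-20% at D52 and 6-17% at D14 (change reading), and to about 0-3% at D52 and 7-17% at D7 (covariate-only reading).

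A third reading compares D52 levels with D0 still among the responses. In the five floor cases it gives .025-.063 at D52, and D0 imbalance still explains 46-79% of the contrast.

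**Step 3: why the baseline covariate does not help the change contrast.** It adds the same amount to a patient's D0 and D52 predictions, so it drops out of the difference.

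**Step 4: the mechanism.** In the fast case the mean of the four visit variances is (420.3 + 116.6 + 54.8 + 12.3)/4 = 151, a common SD of 12.3 set against 20.5 at D0 and 3.5 at D52. With D0 out of the response it is (116.6 + 54.8 + 12.3)/3 = 61, SD 7.8: too wide for D52 (3.5) and too narrow for D7 (10.8, before adjusting for D0).

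**Step 5: does a separate variance repair it?** On the same data, in the five floor cases, a change test with its own variance has D52 error .046-.052. A single-visit ANCOVA of D52 on D0 has .030-.048.

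**The case against.** **The change contrast is not written in the SCAT5 text.** This is correct. SAP 8.5.1.3 says only that the visits are analysed; change from D0 is inferred from the reused template. A reader might infer that the plan certainly inflates false positives at D14 and D52. The documents do not support that, since one reading is conservative at D52. What stands is that both the change and the covariate-only readings misstate the error at some visit.

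**The floor is an inference.** This is also correct. The protocol speaks of symptoms resolving and of lasting effects, and gives no scores. The SCAT5 form also has athletes rate their usual state at baseline, and items such as fatigue or irritability can be present in ordinary life. Zero symptoms is therefore stricter than recovery.

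**A linear model is not wrong merely because scores are bounded.** I accept this. Step 5 shows that the error rate recovers once the variance is not pooled, so the floor and skewness alone do not invalidate a linear analysis.

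**A reader might conclude that the arm comparison should rest on the symptom-free proportion or an ordinal mixed model.** The documents do not support this. Their endpoint is the evolution of symptom number and severity. Which method has more power depends on the assumed effect:
- With 40% v 75% symptom-free at D14 and equal severity among the unresolved, the Newcombe interval detects the difference in about 75% of trials and a baseline-adjusted single-visit linear analysis in 47%.
- With 40% at zero in both arms and unresolved means of 20 v 8, the linear analysis has 61% and the proportion 6%.
- At D52, 80% v 90% symptom-free gives the proportion only 16% power.

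An ordinal mixed model in 50 patients has not been tested here.

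**Stakes are limited.** SCAT5 is an unadjusted secondary endpoint in a pilot with a safety primary endpoint, and confirmation is left to later sham-controlled work.

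**Conclusion.** The concern holds as a specification defect: the arm contrast is unclear, and one residual variance is pooled over visits that should differ greatly in spread. On the template's change reading, about 80-95% of the variance of the D52 arm difference is chance D0 imbalance, and the 5% test errs at about 8-20% at D52 and 6-17% at D14. With D0 as covariate only, the error is about 0-3% at D52 and 7-17% at D7.

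The figures are conditional on the assumed SCAT5 distributions: D0 severity mean 20-40 with SD about 12-25, and 40-60% at zero by D14 and 80-90% by D52. Only the D52 share has direct support, from the protocol's 10-20% with lasting effects. The no-floor control shows that the imbalance problem disappears if scores do not collapse (7% of the contrast, D52 error .013). Even after correction, D52 carries little information on the arms: 10-20% of 25 is only about 3-5 unresolved patients per arm.

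**What to change.** In SAP 8.5.1.3:

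1. Use D7, D14 and D52 as the responses, with D0 SCAT5 as a covariate only.
2. Allow a separate variance at each visit, through an unstructured covariance across the three visits or an ANCOVA at each visit.
3. Report the adjusted arm difference with 95% CI at D7, D14 and D52, and adapt the template so that D0 is not the reference for the contrast.
4. Add a supportive table for D7, D14 and D52: number and % of patients with a total symptom count of 0 by arm, the between-arm difference and a 95% Newcombe CI. Note that zero is a strict threshold because some items can be present in usual life.
5. List the baseline covariate and these changes in SAP section 10.

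The cost is a few more covariance parameters, some SAP wording and one extra table from data already collected. The primary ADE analysis does not change.
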